### **Accrual**

The MDD participants will be primarily recruited from the Outpatient Clinics of the University of Pennsylvania, including the Mood and Anxiety Disorders program, student health and the general adult psychiatry programs. These programs see 400+ new patients with depressive disorders each year and contributed 72 unmedicated MDD participants across 30 months to the recently completed noninferiority study of CCBT. Should the need arise, we also can recruit from the Philadelphia VA Medical Centers Behavioral Health Laboratory (PVAMC-BHL). As the BHL continuously screens from the primary care clinical population of the PVAMC, it will serve as a rich secondary recruitment resource for individuals for this study. As an example, from August 2013 to August 2014, 1,298 individuals between ages 18 and 45 completed assessments within the BHL. Of the 1,194 individuals who completed full assessments, approximately 29.4% screened positive for MDD, providing an ample participant base from which to recruit. We thus anticipate no difficulty enrolling depressed patients into this study. Up to 120 participants will be consented for participation; however we anticipate that approximately 10% will screen fail and another 10% will either drop out during the study or have unusable scanner data; therefore, we aim to have 60 participants with MDD and 40 healthy control participants who complete the entire study with usable data. C.10.1 Power Analysis For Aim 1, based on our pilot data, we assume that DLPFC in HC is positively correlated with amygdala with correlation of  $r=0.1$ , while in contrast it is negatively correlated in MDD with correlation  $r=-0.1$  (standard deviation 0.07). Similarly, our pilot data indicates that IFC in MDD is 70% less correlated with the amygdala than in HC (standard deviation 0.07). Given 60 MDD patients and 40 HC at baseline, we have excellent power (80%) to detect the differences between MDD and HC for their baseline amygdala connectivity in DLPFC and IFC. For subgroup analysis in subjects of each sex separately, we will also have 80% power to detect differences between MDD and HC. Similarly, for baseline task measures, the pilot data indicate up to two-fold higher activation in HC in the four targeted regions (ACC, DLPFC, IFC), indicating that will also have 80% power to detect such differences between MDD and HC (in males and females separately, as well as combining sexes) at the 95% confidence level adjusting for the number of tests. For Aim 2, based on our pilot data, the correlation between IFC and amygdala will increase by 0.09 after CCBT (standard deviation 0.05), and the correlation between precuneus and amygdala will decrease by 0.08 (standard deviation 0.04). We will have 80% power to identify treatment effects comparing the data from 30 MDD patients receiving CCBT in 1-2 weeks with untreated data from the subjects receiving CCBT in 3-4 weeks. We will also have 80% power to detect different treatment effects in males and females separately. For longitudinal changes in activation, we

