which we will also conduct for comparison. Aim 1b: To assess baseline differences between MDD and HC in Emotional Conflict task-induced activation in the dorsal ACC, DLPFC, and IFC, we will apply two approaches: First, perform the voxel-wise general linear model to detect group differences on the AHIF-AHIN contrast; Secondly, we will conduct brain-wide fPCR to explore variations that are associated with depression symptoms while controlling the anxiety symptoms. All analyses will be adjusted for age and sex, and corrected for multiple comparisons by controlling the false discovery rate. Aim 2: Aim 2a: To assess the effect of CCBT on the functional connectome, we will test for differences in amygdala-connectivity between MDD patients who receive treatment immediately (within 1-2 weeks of screening) and those who receive treatment later (within 3-4 weeks of screening). We will examine deficits identified in Aim 1 to compare the MDD groups treated immediately (1-2 weeks) vs. treated later (3-4 weeks) for changes in these regions, adjusting for motion, age and gender. We will also conduct a whole-brain feature search through structured functional principal component analysis (SFPCA) [87]. SFPCA incorporates the longitudinal design complexity and models variation in amygdala-connectivity induced by CCBT through dimension-reduced principal components that are associated with longitudinal changes. Instead of generating contrasts for each hypothesis, it utilizes all available data by explicitly modeling the correlation structures among the observed connectivity maps. Aim 2b: To assess changes of the conflict task-induced activity in ACC, DLPFC, and IFC, we will use the same techniques of SFPCA and targeted mixed-effects modeling adjusting for age and sex. We will also investigate the correlation between the patterns of treatment-induced connectivity and activation normalization. Further, we will investigate the dose-response relationship between total time engaged in CCBT and changes in brain connectivity and activity. Exploratory Aim: We will first use PCR to predict treatment response after CCBT using the baseline amygdala-connectivity map. To avoid overfitting, we will evaluate the prediction performance using bootstrapped cross-validation by iteratively applying learning predictive patterns to 90% of the subjects and testing on the remaining 10%. We will assess treatment response using continuous score changes in depression and anxiety, and remission status (defined by MADRS10 after CCBT). For continuous measures of response, we will assess predicted mean-square error (MSE) for symptomatic change in two ways: first, we will simply estimate the predictive performance of the principal scores. Next, we will compare a predictive model based on regression with only baseline depression scores to a model with both baseline scores and principal scores to assess the added value of the imaging markers. For remission status, we will assess both the predictive performance of the principal scores and the added value of these markers above baseline depression scores and other demographics (age, sex, socio-economic status) using receiver-operator characteristic (ROC) curve analysis. Differences in the performance will be assessed by building confidence intervals for increased area under the curve (AUC) using bootstrapped cross-validation. We will apply the same techniques to the contrast of parameter maps from the conflict task, as well as to the cortical thickness maps. We will build second stage meta-classifiers that integrate the patterns found using these functional and structural imaging measures using generalized linear modeling, which will allow us to integrate the imaging predictors with age, sex, and other demographic information. To assess the importance of baseline executive function measures, we will examine the improvement in predictive performance by including these into the meta-classifiers. Other machine learning algorithms such as support vector machines and random forests, as well as collaborative learning will also be explored to achieve optimal performance. We will also assess the amount of model improvement by incorporating joint resting-state, task-based activation, and cortical thickness patterns into the previous PCR model by calculating c-statistics and prediction indices (such as net reclassification improvement and integrated discrimination improvement etc.) sequentially. Finally, we will investigate sparse patterns of association between imaging measures and depression phenotypic measures using sparse canonical correlation analysis. \*\*\*NOTE REGARDING DATA ANALYSIS WITH PROTOCOL 826910\*\*\* Procedures and data elements are the same between #826910 and #832295, therefore they will not need to be reconciled. The data from the two study will be added together. Participant data from the Immediate CCBT group from #826910 and the early CCBT group from #832295 will be grouped together for analysis. Participant data from the Wait-list Followed by CCBT group from #826910 and the delayed CCBT group in #832295 will be grouped together for analysis.

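### Category-free net reclassification improvement leans towards useless imaging scores once the reference model discriminates moderately; added imaging blocks should be judged on held-out c-statistic and Brier score

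*Combined protocol and SAP*

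**What the plan says.** All of this is in the Analysis Plan (C.10), Exploratory Aim, of the combined protocol and SAP. The first step predicts response from the baseline amygdala-connectivity map by principal component regression: "To avoid overfitting, we will evaluate the prediction performance using bootstrapped cross-validation", learning on 90% of subjects and testing on 10%. Continuous response is scored by predicted mean-square error. Remission is assessed by ROC analysis, with differences judged by "building confidence intervals for increased area under the curve (AUC) using bootstrapped cross-validation".

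A later sentence measures the improvement when all three imaging types (resting-state, task activation, cortical thickness) enter that first regression model. The method named is "calculating c-statistics and prediction indices (such as net reclassification improvement and integrated discrimination improvement etc.) sequentially". That sentence does not say:

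- whether NRI is category-free or categorical, or what the risk cut-offs are;
- what test, threshold or rule defines an improvement;
- whether these indices are computed on held-out predictions.

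Accrual gives the sample: "we aim to have 60 participants with MDD and 40 healthy control participants who complete the entire study with usable data". Only the 60 MDD patients have a treatment outcome to predict.

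**The concern.** Category-free NRI records only whether each patient's predicted risk moves up or down. It ignores how far the risk moves and whether the new value is closer to the truth. In a small sample, adding noise scores makes the fitted model too extreme, so predicted risks are pushed outward along the direction the real predictors already point. If those predictors carry some signal, remitters tend to move up and non-remitters down, and the index counts this as improvement.

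The step is meant to show how much each kind of imaging adds. An index that leans positive for useless scores can suggest a multimodal gain where the larger model predicts worse. The Overall objectives tie these algorithms to better treatment assignment, so a spurious gain could misdirect follow-on work. It would not touch the primary outcomes of Aims 1 and 2.

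**Working it through.** The documents give no NRI value, threshold or reference AUC, so there is no stated figure to reproduce. The check is by reasoning and simulation with true added value set to zero.

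**Inputs from the documents.** 60 MDD patients (Accrual); a 90/10 split, so 0.9 × 60 = 54 to train and 6 to test; three imaging types added in sequence. **Assumed:** remission 35-50%; 3 or 5 noise scores per imaging block unless noted; reference AUC 0.5-0.8; logistic models.

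**Formula.** Category-free NRI = [P(up | remitter) − P(down | remitter)] + [P(down | non-remitter) − P(up | non-remitter)].

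**Mechanism.** Suppose the larger model only stretches every risk away from the centre. Let *a* be the share of remitters above the centre and *b* the share of non-remitters below it. Then NRI = (2a − 1) + (2b − 1) = 2(a + b − 1). With no discrimination, a + b = 1 and NRI = 0. With discrimination, a + b > 1 and NRI is positive, although the ranking, and so the AUC, has not changed. A stretch about 0.5 carries nobody across 0.5, so NRI cut at 0.5 gains nothing.

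**Simulation 1: 5 noise scores, scored on a large independent set.**

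| Reference AUC | Mean category-free NRI | Positive in | Mean AUC change |
|---|---|---|---|
| 0.6 | +0.014 | 60-62% | −0.037 to −0.040 |
| 0.7 | +0.06 | 75-76% | −0.055 to −0.058 |
| 0.8 | +0.16 | 85-88% | −0.043 to −0.047 |

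At reference AUC 0.5 the mean was about 0. When both models were recalibrated on the test set, NRI became clearly negative (−0.23 at AUC 0.6, −0.39 at 0.7, −0.49 to −0.50 at 0.8). The positive lean therefore comes from miscalibrated, overfitted risks.

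**Simulation 2: 60 patients, 54/6 cross-validation, three noise blocks.**

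| Reference AUC | Mean NRI per block | Positive in | z > 1.96 per block |
|---|---|---|---|
| 0.5-0.6 | −0.03 to +0.03 | no clear bias | – |
| 0.7 | −0.02 to +0.11 | 46-64% | 4-10% |
| 0.8 | +0.07 to +0.27 | 58-76% | 12-28% |

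At 0.7-0.8 the mean AUC fell by 0.01-0.05 and the Brier score worsened by 0.015-0.052.

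**Simulation 3: 60 patients, about 40% remission, one real predictor plus three demographics without effect, 10-fold held-out predictions, three noise blocks.** Here AUC means the held-out AUC of the reference model.

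- AUC 0.54: mean NRI −0.01 to +0.05.
- AUC 0.63: mean NRI +0.04 to +0.07.
- AUC 0.71: mean NRI +0.08 to +0.17, positive in 58-68%.
- The mean AUC change was negative in every setting (−0.004 to −0.055), and the Brier score improved in only 6-13%.

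A further null run with 60 patients and 10-fold held-out predictions gave mean NRI of about +0.02 to +0.21 at held-out reference AUC 0.63-0.71. AUC fell by 0.01-0.04 and the Brier score improved in 4-16% of runs. At AUC about 0.52 the mean NRI was near zero.

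**Other indices.** For reference AUC 0.7-0.8, NRI cut at 0.5 was about zero or negative on an independent set (−0.07 to about 0) and −0.01 to −0.06 cross-validated. Three-category NRI was −0.01 to −0.06 cross-validated. Held-out integrated discrimination improvement was about zero or slightly negative.

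**If computed in-sample.** Five noise scores gave mean category-free NRI of +0.47 to +0.62, positive in 98-99% of runs.

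**Illustrative test rates.** One-sided nominal error is 2.5% per step. Over three steps, treated as independent, it is 1 − 0.975³ = 7.3%. In simulation 2 at least one noise block passed z > 1.96 in 14-23% of datasets (AUC 0.7) and 31-42% (AUC 0.8).

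**The case against.** The strongest reply has four parts.

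1. **Form.** The plan names NRI without saying category-free, and categorical NRI does not reward noise in most settings. A reader might infer that NRI in any form favours noise; the results do not support that. What stands is that, with no categories defined, the category-free form is the natural reading and the plan leaves it open.
2. **Strength of the reference model.** With a weak reference model the mean bias is about nil, and the documents give no AUC. This stands as a limit on size. The bias does grow with a useful reference model, which is where a claim of added value would matter most.
3. **No decision rule.** A reader might infer that the plan will declare useless imaging an improvement at the error rates above. It states no z-test, threshold or selection rule, so those rates are only illustrative.
4. **Safeguards.** C-statistics stand first in the same sentence, and an AUC confidence interval is planned earlier. They would often contradict a spurious NRI: a nominally significant NRI at any step without an AUC rise occurred in 1-4% of null datasets at reference AUC 0.52, 5-9% at 0.65 and 9-26% at about 0.73. This limits the harm. It does not settle which index prevails when they disagree: in simulation 3 at AUC 0.71, 35-47% of noise blocks had positive NRI while AUC fell.

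A reader might also infer that the indices will be computed in-sample. The plan does not say so. It only fails to repeat the held-out scheme here.

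**Conclusion.** The point holds in a limited form. Read as category-free and computed on held-out predictions from about 60 patients, NRI leans positive for useless imaging scores once the reference model reaches a held-out AUC of about 0.63. The mean is about +0.02 to +0.2, positive in roughly 55-72% of datasets, while AUC and Brier score worsen on average. Results at the lower end vary: in simulation 2 at reference AUC 0.7 some blocks averaged slightly below zero. The lean is near zero for a weak reference model and absent for NRI cut at 0.5. In-sample calculation, which the plan does not exclude, would inflate every index.

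The size rests on assumed reference AUC, remission rate and number of scores, and on simple logistic models standing in for the planned regression. Importance is minor: this is one of several indices in an Exploratory Aim.

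**What to change.** Amend the sequential step in the Analysis Plan to state that:

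- every index is computed on the held-out predictions;
- each added imaging block is judged by the change in held-out c-statistic with its confidence interval, plus the change in held-out Brier score or log-likelihood. The Brier score is the counterpart for remission of the mean-square error already planned for continuous response;
- NRI is dropped, or shown as descriptive only, with its form defined and the remitter and non-remitter parts reported separately.

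The cost is a sentence or two of text. The same held-out predictions serve and no new data are needed. The downside is the loss of a familiar index and gains that look less favourable.

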#### Number of subjects enrolled at Penn since the study was initiated

4

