**Modification Summary**

Please describe any required modification to the protocol. If you are using this form to submit an exception or report a deviation, enter 'N/A' in the box below.

Modifying study procedures to include an additional 15 minute computer task. Informed consent forms have been modified to include information about this computer task. Two key study personnel have been added to the study.

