## Procedures

Participants will complete a phone screen or a online self-report screener to determine eligibility. If the participant is eligible, they will be scheduled for an in-person screening visit. Information collected during the pre-screening will not be used in the data analysis; pre-screening information will be collected and retained in REDCap. Participants will be asked to authorize the release of the medical records for the purposes of determining their eligibility for this study. Individuals who are patients in the Penn system will be asked for verbal consent during the pre-screening to release their PennChart electronic medical record. Data from the PennChart electronic medical record will be viewed only. The information will not be downloaded or stored. Individuals who are not in the Penn system will be asked to complete an medical record release authorization form at the screening visit after their have signed the informed consent. Upon receipt of their medical records, personal health information and identitifiers will be redacted to mitigate the risk of lost of confidentiality and privacy. Visit 1 (Screening) - all participants will have the study described to them in detail, including the risks and study procedures as outlined in the informed consent form and will sign the ICF and HIPAA authorization, prior to any study procedures being completed. Participants will be screened for symptoms of psychological disorders and severity of major depressive symptoms by a trained research team member. If determined eligible, HEALTHY CONTROLS will be scheduled for return to complete a 1-hour fMRI scan and baseline visit, in which self-report measures, including reports of mood, behavior, and thoughts will be collected, as well as neuropsychological testing. Healthy controls will begin "Remote Monitoring" by being given an actigraph to wear 24 hours a day for 8 weeks and will have Beiwe installed on their cell phones. The mobile application has two elements: Passive data collection: Behavior data is gathered unobtrusively through a background process on the mobile device. The background process is launched automatically by the application once the user logs in. After the initial logon, the process continues to be automatically launched whenever it is not already running (on phone restart or other events that terminate the process). Active data collection: Surveys and other self-report data are gathered through user input. This is achieved in two ways: (i) the user receives a notification that a survey is available and upon launch the application and they are shown all the surveys available at that time. Controls will return for an in-person visit following the 8 weeks of remote monitoring to return actigraph, have Beiwe disabled from cell phone, and receive ClinCard compensation. If determined eligible at screening, MDD (EXPERIMENTAL GROUP) participants will begin CCBT treatment within 4 weeks after completing baseline assessments. Half of the depressed participants will begin 8 weeks of CCBT within 2 weeks from completing baseline assessments (Early CCBT), and the other half after 2 weeks from completing pre-treatment baseline assessments (Later CCBT). Participants are randomly assigned to either (1) Early CCBT or (2) Later CCBT based on the a number randomly generated by the computer. All MDD participants will receive 8 weeks of CCBT within 4 weeks from completing baseline assessments. Participation duration may vary depending on the scheduling availability of the therapists, participants, and also our facilities. All CCBT participants will be scheduled for return for Visit 2 to complete a 1-hour fMRI scan and baseline visit, in which self-report measures, including reports of mood, behavior, and thoughts will be collected, as well as neuropsychological testing. Participants will begin "Remote Monitoring" by being given an actigraph to wear 24 hours a day for 8 weeks and will have Beiwe installed on their cell phones (see above for details of Beiwe). MDD subjects who are scheduled to begin CCBT after 2 weeks (Later CCBT) will complete an additional fMRI scan when they return to begin treatment. For the Later CCBT participants, the 2nd MRI scan is at least 2 weeks and up to 4 weeks from the 1st pre-treatment MRI scan. MDD participants will also have Ethica installed on their cell phones at their and complete 1 question/day regarding Good Days Ahead adherence on Ethica for 8 weeks when they being CCBT treatment. Again, this will be dependent on when subjects begin CCBT. Ethica will be used for active data collection, which includes surveys and other self- report data are gathered through user input. This is achieved in two ways: (i) the user receives a notification that a survey is available and upon launching the application they are shown all the surveys available at that time. Participants will complete Good Days Ahead (GDA) computer training at their CCBT Week 1 visit. They will have CBT Clinical Contact with a licensed psychologist/psychiatrist at Weeks 1, 2, 4, 6, 8, & 9 of treatment. Additionally,

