
outcome measures will be assessed by an independent clinical evaluator (without knowledge of treatment assignment) at every in-person study visit. Weeks 3, 5 & 7 will be completed off-site (at home, preferably). Participants will have a final 1-hour fMRI scan at end of study during CCBT Week 9, in which self-report measures, including reports of mood, behavior, and thoughts will be collected, as well as neuropsychological testing. Both MDD and healthy control participants will complete a 15-minute computer task called "The Foraging Task" examining their responses to rewards during Visit 2. Foraging task Details: At the beginning of each trial, participants hold fixation on a central fixation square for 2.5 seconds. Afterwards the square turned green signaling they could make a choice. They needed to move the joystick to the nearby bush to earn a reward, displayed after a short period of time called handling time. On subsequent trials, participants could choose to go back to the same bush (stay). Reward however diminished for every subsequent attempt. At any point they could decide that the reward they are getting in that bush is not high enough and that they wanted to travel to a new non-depleted bush. If they wanted to leave and go to the next bush, they needed to move the joystick to the square on the other side of the screen, and then the bushes started sliding down as if they were traveling to the next bush. The amount of time it took to travel to the next bush depended on the environment. In one block it took 5s to travel to the next bush and in another it took 20s. There were unlimited number of bushes in the environment but they had a finite time in each one (6 min x 2 blocks). The remuneration would be based on the amount of berries they have collected by the end of the session. PLEASE SEE ATTACHED TABLES SHOWING SCHEDULE OF PROCEDURES FOR EACH STUDY GROUP. PARTICIPANTS WHO ARE ALSO PARTICIPATING IN THE 824132 PROTOCOL WILL PARTICIPATE IN BOTH STUDIES SIMULTANEOUSLY. VISITS 1&2 OF THE CURRENT PROTOCOL ARE MOSTLY ENCOMPASSED WITHIN THE FULL 824132 PROTOCOL, WITH THE EXCEPTION OF SOME SELF-REPORT MEASURES AND ANY CCBT PROCEDURES THAT WOULD OCCUR AT VISIT 2 FOR THE IMMEDIATE CCBT GROUP; THEREFORE THE DURATION OF THE FIRST 2 STUDY VISITS FOR DUAL PARTICIPANTS WILL BE SLIGHTLY LONGER THAN FOR THOSE WHO ONLY PARTICIPATE IN THIS CCBT PROTOCOL.

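### Data from 826910 are added to 832295 as if identical, with no reconciliation and no source-protocol term in any stated model

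*Combined protocol and SAP*

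**What the plan says.** The note on protocol 826910 at the end of the Analysis Plan says "Procedures and data elements are the same between #826910 and #832295, therefore they will not need to be reconciled". It continues: "The data from the two study will be added together". The arms are matched by name. For the first arm, "Participant data from the Immediate CCBT group from #826910 and the early CCBT group from #832295 will be grouped together for analysis". For the second, "Participant data from the Wait-list Followed by CCBT group from #826910 and the delayed CCBT group in #832295 will be grouped together for analysis".

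Target population gives the division of the sample: 37 MDD and 24 control participants are to come from 832295, towards a total of 60 and 40.

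The adjustments named in the Analysis Plan are motion, age and sex for Aim 1a, age and sex for Aim 1b, motion, age and gender for Aim 2a, and age and sex for Aim 2b. Source protocol is not among them.

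The Modification Summary describes the present change as "Modifying study procedures to include an additional 15 minute computer task". Procedures says that MDD and control participants do this task, "examining their responses to rewards during Visit 2". The same section says of that visit: "All CCBT participants will be scheduled for return for Visit 2 to complete a 1-hour fMRI scan and baseline visit". The form gives 4 under "Number of subjects enrolled at Penn since the study was initiated", so the procedures changed after 832295 had begun to enrol.

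**The concern.** Pooling two protocols by simple addition is safe if they are the same in everything that affects the outcome, or if both arms draw the same share from each. The plan asserts the first and gives no figures for the second.

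Three things in the documents make the assertion less than self-evident. A procedure is being added to 832295 at the visit that holds the baseline scan. The 826910 wait-list is never described: its wait length, scan interval and allocation method are all absent. And the 832295 group it joins has no single definition.

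What is at stake is mainly Aim 2. The Later group's untreated scans are the comparator for the treatment effect (Primary outcome variable(s); Accrual). If scan-to-scan change differs between protocols for reasons other than treatment, and the arms draw unequal shares from 826910, part of that difference is reported as an effect of CCBT.

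**Working it through.** **The plan's own count.** 37 + 24 = 61, which matches the figure under Subjects enrolled by Penn Researchers.

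**Share from 826910.**
- MDD: 60 − 37 = 23, and 23/60 = 38.3%.
- Controls: 40 − 24 = 16, and 16/40 = 40.0%.
- Overall: 39/100 = 39%.

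**Aim 1.** The shares differ by 40.0 − 38.3 = 1.7 points. Even an assumed between-protocol difference of 0.5 SD would move the MDD-control contrast by only 0.017 × 0.5 ≈ 0.01 SD.

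**Aim 2.** Take 30 patients per arm (Accrual gives 30 early; Procedures assigns half to each group). If *a* of the 23 patients from 826910 are in the early arm, the arms differ in 826910 share by (a − (23 − a))/30 = (2a − 23)/30. Bias in the unadjusted contrast is that fraction times the between-protocol difference in change. The documents give neither quantity. The splits below and the range of 0.2 to 0.5 SD are assumptions.

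| Early/Later split of the 23 | Share difference | Bias at 0.2 SD | Bias at 0.5 SD |
|---|---|---|---|
| 11.5/11.5 (even) | 0 | 0 | 0 |
| 8/15 | 7/30 = 23% | 0.05 SD | 0.12 SD |
| 5/18 | 13/30 = 43% | 0.09 SD | 0.22 SD |

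For scale, the effects assumed in Accrual are 0.09/0.05 = 1.8 SD (IFC) and 0.08/0.04 = 2.0 SD (precuneus), if those SDs are the ones that apply to the contrast.

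**Cost of adjusting.** Unstratified information is 30 × 30/60 = 15. Stratified information is the sum of n₁n₂/(n₁ + n₂) over the two protocols.
- 8/15: (8 × 15)/23 + (22 × 15)/37 = 5.22 + 8.92 = 14.14, so variance rises by 15/14.14 − 1 = 6%.
- 5/18: (5 × 18)/23 + (25 × 12)/37 = 3.91 + 8.11 = 12.02, so variance rises by 25%.
- Even split: no increase.

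With 30 per arm, 0.09 and SD 0.05, two-sided 5%, power stays above 99% in all three cases. The plan's stated 80% does not reproduce from these inputs, which give over 99.8% without adjustment. It reads as a floor and does not affect this point.

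**Later-group timing in 832295, side by side.**
- Abstract: an extra pre-treatment scan for those starting after 3 weeks; appointments by first availability.
- Primary outcome variable(s): a wait of 3-4 weeks.
- Design: start after 2 weeks from the first MRI, and also 15-28 days from screening; assignment at random.
- Procedures: start after 2 weeks from baseline assessments; assignment at random.
- Analysis Plan: 3-4 weeks from screening.

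The 3-4 week range can be read as days 15-28, so part of this may be wording. The different starting points, and the 3-week threshold against the 2-week one, remain.

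**The case against.** The strongest reply is that nothing in the documents shows the protocols to differ in a way that matters, and that the bias range starts at zero and rests on assumed inputs. That is correct. Even 0.22 SD is only 11-12% of the effects the plan expects (0.22/2.0 and 0.22/1.8), and no conclusion has been shown to change.

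Four stronger readings are tempting and should not be drawn.

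- **That the two delayed groups are defined differently.** The documents give two labels and no definition for 826910. Equivalence is unverified, not disproved. The inconsistency that can be shown lies inside 832295.
- **That 826910 lacked the added task.** This is a fair inference from its addition now, but no section says so. The task also appears in no listed outcome or analysis, so it could matter only through its effect on other Visit 2 measures.
- **That the order of task and scan is unspecified.** The narrative does not give it, but Procedures refers to attached schedules and General Attachments lists them. They were not available for this review and may settle it. Both 832295 arms do the task at Visit 2, so a common effect on the baseline scan would largely cancel in the Early-Later difference in change. It would not cancel in the pre-post comparison, for which patients serve as their own controls.
- **That delayed patients should be regrouped by their actual untreated interval.** Design and Procedures randomise them. Regrouping on an interval driven partly by scheduling would give up that protection.

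What survives is that the plan asserts sameness where it could show it, and leaves out a term that costs very little.

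**Conclusion.** The point holds as a gap in the pooled analysis, not as a demonstrated bias. Thirty-nine per cent of the sample comes from a protocol whose groups are not described, and no stated model allows for it. Aim 1 is close to balanced and little affected. For Aim 2 the exposure cannot be computed, because the arm split of the 23 patients is missing: it is nil at an even split, and 23% or 43% of any between-protocol difference in change at 8/15 or 5/18. The SD figures depend on the assumed 0.2-0.5 SD difference and on 30 patients per arm. The change is worth making because it is nearly free and because a reader cannot otherwise tell whether simple addition was harmless.

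**What to change.** - Delete the statement that no reconciliation is needed. Replace it with a short table comparing procedures, group definitions, scan intervals and allocation in the two protocols.
- Include source protocol as a covariate or stratum in the pooled Aim 1 and Aim 2 regression and mixed models. Where change is analysed with repeated scans, use protocol-by-time, since a main effect alone does not adjust change.
- Report Early and Later counts by protocol.
- Add a protocol-by-arm sensitivity analysis for Aim 2, reported as an estimate with its interval. With near-even splits its standard error is about √(2/11.5 + 2/18.5) = 0.53 SD, so a non-significant result would not establish equivalence.
- Keep patients in their assigned Early or Later group. Give actual untreated scan-to-scan intervals descriptively or in a sensitivity analysis.
- Reconcile the passages on Later-group timing and on assignment (Abstract, Primary outcome variable(s), Design, Procedures, Analysis Plan).
- Confirm that the Visit 2 task is done after the scan, so that it cannot enter the pre-post change.

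The cost is some plan wording, one or two degrees of freedom, and a loss of precision only if the arms are unbalanced by protocol (6% more variance at 8/15, 25% at 5/18).
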